15.5 Etoposide (VePesid®, Toposar®, VP16)

Refer to the package insert for complete prescribing information.

- 15.51 **Background:** Etoposide has been shown to delay transit of cells through the S phase and arrest cells in late S or early G2 phase. The drug may inhibit mitochondrial transport at the NADH dehydrogenase level or inhibit uptake of nucleosides into HeLa cells. It is a topoisomerase II inhibitor and appears to cause DNA strand breaks. Etoposide does not inhibit microtubular assembly.
- 15.52 **Formulation:** Commercially available for injection as:
Injection, solution: 20 mg/mL (5 mL, 25 mL, 50 mL)
- 15.53 **Preparation, storage, and stability:** Refer to package insert for complete preparation and dispensing instructions. Store intact vials at room temperature of 25°C (77°F); do not freeze. Protect from light. Etoposide should be diluted to a concentration of 0.2-0.4 mg/mL in D5W or NS for administration. Diluted solutions have concentration-dependent stability; more concentrated solutions have shorter stability times. Precipitation may occur with concentrations > 0.4 mg/mL. Following dilution 0.9% Sodium Chloride or D5W to concentrations of 0.2-0.4 mg/mL, then drug is chemically stable for 96 and 24 hours at room temperature respectively.
- 15.54 **Administration:** Refer to the treatment section for specific administration instructions. Administer standard doses over at least 30-60 minutes to minimize the risk of hypotension.
- 15.55 **Pharmacokinetic information:**
Distribution: V_d : 7-171 L/m²; poor penetration across the blood-brain barrier; CSF concentrations <5% of plasma concentrations
Protein binding: 94% to 98%
Metabolism: Hepatic via CYP3A4 and 3A5, to various metabolites.
Half-life elimination: Terminal 4-11 hours
Excretion: Urine (56%; 45% as unchanged drug) within 120 hours; feces (44%) within 120 hours
- 15.56 **Potential Drug Interactions:**
Metabolism/Transport Effects: Substrate of CYP1A2 (minor),

CYP2E1 (minor), CYP3A4 (major), P-glycoprotein; **Inhibits** CYP2C9 (weak), 3A4 (weak)

Ethanol/Herb/Nutraceutical Interactions: Avoid ethanol (may increase GI irritation). Avoid concurrent St John's wort; may decrease etoposide levels.

- 15.57 **Known potential adverse events:** Consult the package insert for the most current and complete information. **U.S. boxed warning: Severe dose-limiting and dose-related myelosuppression with resulting infection or bleeding may occur.**

Common known potential toxicities, > 10%:

Dermatologic: Alopecia

Gastrointestinal: Nausea/vomiting, anorexia, diarrhea

Hematologic: Leukopenia, thrombocytopenia, anemia

Less common known potential toxicities, 1% - 10%:

Cardiovascular: Hypotension

Gastrointestinal: Stomatitis, abdominal pain

Hepatic: Hepatic toxicity

Neuromuscular & skeletal: Peripheral neuropathy

Miscellaneous: Anaphylactic-like reaction

Rare known potential toxicities, <1% (Limited to important or life-threatening):

Amenorrhea, blindness (transient/cortical), cyanosis, extravasation, facial swelling, hypersensitivity, hypersensitivity-associated apnea, interstitial pneumonitis, laryngospasm, maculopapular rash, metabolic acidosis, MI, mucositis, myocardial ischemia, optic neuritis, perivasculitis, pruritus, pulmonary fibrosis, radiation-recall dermatitis, rash, reversible posterior leukoencephalopathy syndrome (RPLS), seizure, Stevens-Johnson syndrome, tongue swelling, toxic epidermal necrolysis, toxic megacolon, vasospasm

- 15.58 **Drug procurement:** Commercial supplies. Pharmacies or clinics shall obtain supplies from normal commercial supply chain or wholesaler.

15.59 **Nursing Guidelines:**

15.591 Monitor CBC. Neutropenia may be severe. Instruct patients to report any sign/symptoms of infection to the health care team.

15.592 Rare myocardial infarctions have been reported in patients who have received prior mediastinal XRT. Instruct patient to report any chest pain, or racing of the pulse to the health care team immediately.

15.593 Advise patient of possible mild, reversible alopecia.

- 15.594 A rapid infusion may cause hypotension and/or allergic reaction; administer medication over 30-60 minutes and monitor VS during administration.
- 15.595 Drug is a radiosensitizer and irritant. Assess IV patency before and throughout infusion. Patients who have received prior radiation may experience radiation recall. Assess skin in these areas and monitor closely. Instruct patient to report any rash or skin changes to the health care team immediately.
- 15.596 Anaphylaxis is rare but has been observed. Symptoms may include hypotension, bronchospasm, fever, or chills. Have the anaphylaxis tray available.
- 15.597 Nausea and vomiting are usually mild. However the incidence is increased with oral administration. Premedicate with antiemetics as ordered and monitor for their effectiveness.
- 15.598 Instruct patient in importance of maintaining adequate hydration to avoid hyperuricemia.
- 15.599a Monitor liver function tests.
- 15.599b VP16 solution is oil based and settles to bottom of bag or drip chamber. Be sure to agitate bag to avoid reaction to concentrated solution. Reaction would include flushing, shortness of breath, back pain, and anxiety.
- 15.599c Advise patient that facial flushing is common and may occur even after administration.
- 15.599d Monitor INR closely in patients on warfarin therapy, as VP-16 may increase PT time.
- 15.599e May increase the toxicity of methotrexate or cyclosporine (cytotoxicity) when given concurrently.

16.0 Statistical Considerations and Methodology

- 16.1 Overview: This is a phase I/II study designed to evaluate the safety and efficacy of the addition of lenalidomide to R-ICE (R2-ICE) for patients with first relapse or primary refractory diffuse large B-cell lymphoma. The phase I portion is designed to determine the maximally tolerated dose (MTD) and toxicity profile of lenalidomide in combination with R-ICE using the standard cohort 3+3 design. The phase II portion will utilize a one-stage design with an interim analysis to evaluate the overall response rate of R2-ICE.
- 16.11 Primary Endpoint:
The primary endpoint of the phase I portion of this trial is to assess the maximum tolerated dose (MTD) of the addition of lenalidomide to R-ICE. The primary endpoint in the phase II portion of this trial is the overall response rate after two cycles of treatment. A response will be defined as a CMR or PMR noted as the

objective status after two cycles of treatment. Throughout Section 16.0, response will be considered synonymous with “success”, unless specified otherwise. All patients meeting the eligibility criteria who have signed a consent form and have begun treatment will be evaluable for overall response, with the exception of patients who are determined to be a major treatment violation.

16.12 Sample Size:

The phase I portion of this study is expected to require a minimum of 9 and a maximum of 12 evaluable patients. DLBCL patients treated at the MTD in the phase I portion will also be included in the phase II portion. Additional evaluable patients will be accrued at the MTD dose level for a total of 45 evaluable patients in the phase II portion of this study. If a patient is found to be ineligible after enrollment due to central pathology review, they will be replaced. We anticipate accruing an additional 6 patients (2 phase I, 4 phase II) to account for ineligibility, cancellation, major treatment violation, or other reasons. Maximum projected accrual is 63 patients.

16.13 Accrual Rate and Study Duration:

The anticipated accrual rate is 4-5 evaluable patients per month. It is anticipated that it will likely take about 2 months to enroll, treat, and evaluate each set of 3 patients in the phase I portion of this study. The phase I portion is expected to take between 6 and 8 months. Once the phase II portion of the trial begins, we can expect to accrue the required patients in about 10-12 months. We can expect to begin final analysis approximately 1.25 years after beginning the phase II portion, i.e. as soon as the last patient accrued has completed the response evaluation after two cycles of treatment and data entry has been completed. The overall study duration is expected to be a maximum of 2 years.

Phase I Portion

16.2 Study Design: The phase I study is designed to determine the maximally tolerated dose (MTD) and toxicity profile of the addition of lenalidomide to R-ICE in patients with first-relapse or primary refractory diffuse large B-cell lymphoma using the standard cohort 3+3 design. Three patients will be treated at each dose level and observed for a minimum of three weeks (i.e. one full cycle) before new patients are treated. Doses will not be escalated in any individual patient.

16.21 MTD Definition: MTD is defined as the dose level below the lowest dose that induces dose-limiting toxicity (DLT) in at least one-third of patients (at least 2 of a maximum of 6 new patients). A total of 6 patients treated at the MTD will be sufficient to identify common toxicities at the MTD. For instance, those toxicities with an incidence of at least 25% will be observed with a probability of at least 82% ($1-(1-0.25)^6$).

Refer to Section 7.62 for definition of dose-limiting toxicity (DLT).

16.22 MTD Determination:

Dose Escalation: The phase I portion of this study will utilize a standard cohort of three design. The dose levels to which patients will be assigned in sequential

cohorts are described in Section 7.61. The first cohort of three patients will be treated at dose level 1. Decisions on when and how to dose escalate are described below.

- 16.221 Three patients will be treated at a given dose level combination and observed for one cycle (3 weeks) to assess toxicity.
- 16.222 If DLT is not seen in any of the 3 patients, 3 new patients will be accrued and treated at the next higher dose level. If DLT is seen in 2 or 3 of 3 patients treated at a given dose level, then the next 3 patients will be treated at the next lower dose level, if only 3 patients were enrolled and treated at this lower dose level.
- 16.223 If DLT is seen in 1 of 3 patients treated at a given dose level, up to 3 additional patients will be enrolled and treated at the same dose level. If DLT is seen in at least one of these additional three patients (≥ 2 of 6), the MTD will have been exceeded and further accrual will cease to this cohort. If dose-limiting toxicity (DLT) is not seen in any of the three additional patients, 3 new patients will be accrued and treated at the next higher dose level.
- 16.224 After enrolling 6 patients on a specific dose level, if DLT is observed in at least 2 of 6 patients, then the MTD will have been exceeded and defined as the previous dose unless only 3 patients were treated at the lower dose level. In that case, 3 additional patients will be treated at this lower dose level such that a total of 6 patients are treated at the MTD to more fully assess the toxicities associated with the MTD.
- 16.225 Dose de-escalation: If dose-limiting toxicity meets the stopping boundaries set by the above dose escalation algorithm at dose level 1 (for example, more than 1 out of 3 patients or more than 1 out of 6 patients), the next cohort of three patients will be entered at a dose level of -1. If dose level -1 meets the stopping boundaries, the next cohort of three patients will be entered at dose level -2. Further dose re-escalation will depend on the toxicity profile observed at these dose levels, and re-evaluation of the regimen by the study team may be done.
- 16.226 If a patient fails to complete the first cycle of treatment for reasons other than toxicity, the patient will be regarded as inevaluable and will be replaced.

16.227 Operating Characteristics for standard cohort of 3 design: The following table gives the probability of dose escalation at a single dose level as a function of the true probability of DLT at that level using the cohorts of 3 design described above.

True Rate of DLT (%)	Probability of Dose Escalation
10	0.91
20	0.71
30	0.49
40	0.31
50	0.17

16.23 Analysis Plans: All the relevant results pertaining to toxicity, MTD, response, timed endpoints and laboratory correlates will be examined in an exploratory and hypothesis-generating fashion. The small sample size and the heterogeneous patient population associated with phase I studies restricts the generalizability of the results. Any notable statistical result should only be viewed as preliminary evidence for further study in Phase II trials rather than a definitive finding in and of itself.

16.231 Adverse Events Profile

The number and severity of all adverse events (overall and by dose-level) will be tabulated and summarized in this patient population. The Grade 3+ adverse events will also be described and summarized in a similar fashion. This will provide an indication of the level of tolerance for this treatment combination in this patient group.

16.232 Toxicity Profile

The term toxicity is defined as adverse events that are classified as either possibly, probably, or definitely related to study treatment. Non-hematologic toxicities will be evaluated via the ordinal CTC standard toxicity grading. Hematologic toxicity measures of thrombocytopenia, neutropenia, and leukopenia will be assessed using continuous variables as the outcome measures (primarily nadir) as well as categorization via CTC standard toxicity grading.

Overall toxicity incidence as well as toxicity profiles by dose level and patient will be explored and summarized. Frequency distributions, graphical techniques and other descriptive measures will form the basis of these analyses.

16.233 Response Profile

A response is defined to be a CMR or PMR noted as the objective status after 2 cycles of treatment. All patients meeting the eligibility criteria who have signed a consent form and have begun treatment will be evaluable for response.

Responses will be summarized by simple descriptive summary statistics delineating complete and partial responses as well as no response and progressive disease in this patient population.

Phase II Portion

16.3 Statistical Design:

16.31 Decision Rule:

Based on recent data and prior randomized controlled trials in the salvage setting for this patient population, the estimated overall response rate for two cycles of R-ICE based on similar salvage chemotherapy is around 45% (Gisselbrecht, Glass et al. 2010; Kewalramani, Zelenetz et al. 2004; Gyan, Damotte et al. 2013; Stewart, Duan et al. 2011; Thieblemont, Briere et al. 2011; Vacirca, Acs et al. 2014; Crump et al., 2014). For the addition of lenalidomide to be clinically meaningful, our hypothesis is that the addition of lenalidomide in the relapse setting would increase the overall response rate by approximately 20%.

The largest success proportion where the proposed treatment strategy would be considered ineffective in this population is 45%. The smallest success proportion that would warrant subsequent studies with the proposed treatment strategy in this patient population is 65%. The following one-stage design with an interim analysis based on a Simon optimum design (Simon 1989) uses 20 or 45 patients to test the null hypothesis that the true success proportion in a given patient population is at most 45%.

16.311 Interim Analysis Decision Rule: Enter 20 patients into the study. If 9 or fewer successes are observed in the first 20 evaluable patients, we will consider this regimen ineffective in this patient population and terminate this study. Otherwise, if the number of successes is at least 10, we will proceed with accrual.

16.312 Final Decision Rule: Enter an additional 25 patients into the study. If 24 or fewer successes are observed in the first 45 evaluable patients, we will consider this regimen ineffective in this patient population. If 25 or more successes are observed in the first 45 evaluable patients, we may recommend further testing of this regimen in subsequent studies in this population.

16.313 Over Accrual: If more than the target number of patients are accrued, the additional patients will not be used to evaluate the stopping rule or used in any decision making process. Analyses involving over accrued patients are discussed in Section 16.44.

16.314 NOTE: The trial will not be halted while the first 20 patients are evaluated for the interim analysis. However, if the accrual is especially rapid, we may temporarily suspend accrual to prevent missing important acute toxicity patterns.

- 16.32 **Power and Significance Level:** Assuming that the number of responses is binomially distributed, with a significance level of 9%, the probability of declaring that the regimen warrants further studies (i.e., statistical power) and the probability of stopping after the interim analysis under various response proportions can be tabulated as a function of the true response proportion as shown in the table below.

If the true success proportion is...	0.45	0.50	0.55	0.60	0.65
Then the probability of declaring that the regimen is promising and warrants further study is...	0.090	0.249	0.491	0.735	0.900
And the probability of stopping after the interim analysis is...	0.591	0.412	0.249	0.128	0.053

- 16.33 **Other Considerations:** Toxicity, quality/duration of response, and patterns of treatment failure observed in this study, as well as scientific discoveries or changes in standard care will be taken into account in any decision to terminate the study.
- 16.4 **Analysis Plan:** The analysis for this trial will commence at planned time points (see 16.3) and at the time the patients have become evaluable for the primary endpoint. Such a decision will be made by the Statistician and Study Chair, in accord with CCS Standard Operating Procedures, availability of data for secondary endpoints (eg, laboratory correlates), and the level of data maturity. It is anticipated that the earliest date in which the results will be made available via manuscript, abstract, or presentation format is when the last patient has been followed for at least 2 months.

16.41 **Primary Endpoint:**

16.411 **Definition:** The primary endpoint of this trial is the overall response rate after two cycles of treatment. A response will be defined as a CMR or PMR noted as the objective status after two cycles of treatment. All patients meeting the eligibility criteria who have signed a consent form and have begun treatment will be evaluable for overall response, with the exception of patients who are determined to be a major treatment violation.

16.412 **Estimation:** The proportion of successes will be estimated by the number of successes divided by the total number of evaluable patients.

Confidence intervals for the true success proportion will be calculated according to the approach of Duffy and Santner (Duffy and Santner 1987).

16.42 **Secondary Endpoints:**

16.421 **Overall proportion of patients (%) proceeding to stem cell transplant.** **Definition:** The percentage of patients proceeding to stem cell transplant will be estimated by the number of patients who proceed to transplant divided by the total number of evaluable patients. Exact

binomial 95% confidence intervals for the true success proportion will be calculated.

- 16.422 **Complete metabolic response (CMR) rate:** The CMR rate will be estimated by the number of patients with an objective status of CMR divided by the total number of evaluable patients. All evaluable patients will be used for this analysis. Exact binomial 95% confidence intervals for the true CMR rate will be calculated.
- 16.423 **Overall survival (OS):** Survival time is defined as the time from registration to death due to any cause. The distribution of survival time will be estimated using the method of Kaplan-Meier.
- 16.424 **Percentage of Adverse Events (%) categorized based on severity using CTCAE system/organ/class criteria 4.0.** Definition: All eligible patients that have initiated treatment will be considered evaluable for assessing adverse event rate(s). The maximum grade for each type of adverse event will be recorded for each patient, and frequency tables will be reviewed to determine patterns. Additionally, the relationship of the adverse event(s) to the study treatment will be taken into consideration. The frequency and percentage of patients experiencing a particular grade/severity of adverse event would be aggregated and combined data reported.
- 16.43 Correlative Analyses:
- 16.431 **Association of histologic subtype as assessed by pathology and its association with the primary endpoint of the study.** Definition: Histologic subtype (GCB vs.ABC vs. unclassified) from tumor tissue at the start of the study will be evaluated by 2 methods: Hans algorithm by IHC and gene expression profiling using nanostring technology. For each method, the relationship between overall response (responder vs. non-responder) CR rate and subtype will be evaluated using Chi-square tests (or Fisher's exact test if the data in the contingency table is sparse).
- 16.432 **Association of SUV reduction (%) noted on interim PET/CT scan with the primary endpoint of the study.** Definition: This will be evaluated by calculating the percentage (%) SUV reduction noted on interim PET/CT scan and correlated with the overall response (responder vs. non-responder) by using a two sample t-test .
- 16.433 **Association of anatomic size reduction (%) noted on interim PET/CT scan with the primary endpoint of the study.** Definition: This would be evaluated by calculating the percentage (%) anatomic size reduction noted on interim PET/CT scan and correlated with the overall response (responder vs. non-responder) by using a two sample t-test.
- 16.434 **Association of Minimum Residual Disease (MRD) detection in blood with the primary endpoint of the study.** Definition: Minimum residual disease (MRD) detection (positive versus negative as per Sequentia, Inc ® technology) in blood will be evaluated in all patients at baseline and after 2 cycles of treatment. The correlation of MRD detection (positive

vs. negative) with overall response will be evaluated using Chi-square tests (or Fisher's exact test if the data in the contingency table is sparse).

- 16.435 **Association of Minimum Residual Disease (MRD) blood level with the primary endpoint of the study.** Definition: Minimum residual disease (MRD) blood level (measured as per million leucocytes as per Sequentia, Inc.® technology) will be evaluated in all patients at baseline and after 2 cycles of treatment. The correlation of MRD quantification (per million leucocytes as per Sequentia, Inc.®) with overall response (responder vs. non-responder) will be evaluated using two sample t-tests.
- 16.436 **Storage of serum samples for future research.** Description: Serum samples will be collected and stored for future and ongoing research. Some of the initial work for which this would be utilized would include but not limited to studying the serum free light chains (FLC), serum free DNA and the minimal residual disease (MRD). These measures will be summarized descriptively using medians and ranges (continuous measures) or frequencies (categorical measures).
- 16.44 **Over Accrual:** If more than the target number of patients are accrued, the additional patients will not be used to evaluate the stopping rule or used in any decision making processes; however, they will be included in final point estimates and confidence intervals.

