12.0 Descriptive Factors

- 12.1 Phase I only: Dose level (as assigned by registration office): -2 vs. -1 vs. 1 vs. 2
- 12.2 International Prognostic Index (IPI) [Shipp et al, 1993]: low risk (0 or 1 risk factors) vs. low intermediate (2 risk factors) vs. high intermediate (3 risk factors) vs. high (4 or 5 risk factors)

Risk Factors	0 points	1 point
Age	≤ 60 yrs.	> 60 yrs.
Serum LDH	≤ 1 x normal	> 1 x normal
ECOG PS	0 or 1	≥ 2
Stage	I or II	III or IV
Extranodal involvement	≤ 1 site	> 1 site

Total number of risk factors = sum of the number of points for each prognostic factor.

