16.45 Data & Safety Monitoring

- 16.451 The principal investigator(s) and the study statistician will review the study at least every quarter to identify accrual, adverse event, and any endpoint problems that might be developing. The Mayo Clinic Cancer Center (MCCC) Data Safety Monitoring Board (DSMB) is responsible for reviewing accrual and safety data for this trial at least twice a year, based on reports provided by the MCCC Statistical Office.
- 16.452 **Adverse Event Stopping Rule:** The stopping rules specified below are based on the knowledge available at study development. We note that the rule may be adjusted in the event of either (1) the study re-opening to accrual or (2) at any time during the conduct of the trial and in consideration of newly acquired information regarding the adverse event profile of the treatments under investigation. The study team may choose to suspend accrual because of unexpected adverse event profiles that have not crossed the specified rule below.

Accrual will be temporarily suspended if at any time we observe events considered at least possibly related to study treatment (i.e. an adverse event with attribute specified as "possible," "probable," or "definite") that satisfy any of the following:

Phase I (Includes all dose levels in phase I): By the nature of the "cohorts of three" phase I study design, toxicity (i.e., adverse events that are possibly, probably or definitely related to study treatment) stopping

rules are in place for each dose level. Specifically, if 2 or more dose-limiting toxicities (DLTs) are observed during cycle 1 at any given dose level, accrual to that dose level will be stopped, and patients will be accrued to the next lower dose level until a maximum of 6 patients are treated at the lower level. Note that a DLT that affects dose escalation is only that which is observed in the first cycle of treatment. However, all cycles will be reviewed and the study team will determine whether the dose level needs to be adjusted for future patients if ≥ 1 in the first 3 patients OR ≥ 2 in the first 6 patients experience a grade 4 or higher non-hematologic adverse event at least possibly related to treatment over all cycles at any given dose level

Phase II (includes all phase II patients, including Phase I patients treated at the MTD):

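### Section 16.12's phase I maximum of 12 evaluable patients can be exceeded under the written de-escalation rules, which reach 18, so 63 patients and 2 years are assured as maxima only if phase I uses no more than 12

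*Combined protocol and SAP*

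**What the plan says.** Section 16.12 sizes phase I: "The phase I portion of this study is expected to require a minimum of 9 and a maximum of 12 evaluable patients". It adds 45 evaluable patients for phase II and 6 for ineligibility, cancellation and similar losses, and concludes: "Maximum projected accrual is 63 patients". DLBCL patients treated at the MTD in phase I also count among the 45. Section 16.13 allows about 2 months per set of three phase I patients, 6 to 8 months for phase I, about 1.25 years from the start of phase II to final analysis, and at most 2 years overall.

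Four dose levels are defined in 7.61 and listed in 12.1: "Dose level (as assigned by registration office): -2 vs. -1 vs. 1 vs. 2". Accrual starts at level 1. The rules that set the patient count are these:

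- 16.223: after 1 DLT in 3 patients, "up to 3 additional patients will be enrolled and treated at the same dose level". A second DLT among them means the level is exceeded.
- 16.225: if level 1 meets the boundary, the next cohort goes to level -1. Then: "If dose level -1 meets the stopping boundaries, the next cohort of three patients will be entered at dose level -2". On what follows: "Further dose re-escalation will depend on the toxicity profile observed at these dose levels".
- 16.224: when a level is exceeded and the one below has only 3 patients, "3 additional patients will be treated at this lower dose level such that a total of 6 patients are treated at the MTD".
- 16.452: after 2 or more DLTs at a level, "patients will be accrued to the next lower dose level until a maximum of 6 patients are treated at the lower level".

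**The concern.** A stated maximum should be at least as large as the count that the plan's own mandatory rules can produce. De-escalation to levels -1 and -2 is compulsory once the boundary is met. No section caps phase I at 12 or leaves those two levels out of the count. The 63-patient ceiling and the 2-year limit are built on the 12, so they carry a condition that the plan does not state. What is at stake is the accrual ceiling and the timeline.

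**Working it through.** **Reproducing the plan.** Use levels 1 and 2 only.

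- Paths that find an MTD take 9 patients (for example 3 + 6) or 12 (6 + 6), which matches 16.12.
- Accrual: 12 + 45 + 6 = 63.
- Phase I time: 3 to 4 sets × 2 months = 6 to 8 months.
- Study duration: 8 + 15 = 23 months, inside 24.

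The sums are right for that case. Twelve also covers levels 1 and -1 at 6 + 6, and three levels with only one filled to 6 (3 + 3 + 6).

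**Using all four levels.**

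1. Level 1: 1 DLT in 3, then at least 1 in the next 3. Exceeded with 6 patients (16.223).
2. Level -1: the same result. Exceeded with 6 (16.225, 16.223).
3. Level -2: 1 DLT in 3, then 3 more. Takes 6.

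Total: 6 + 6 + 6 = 18. This path does not use 16.224. It excludes re-escalation under 16.225, which has no patient count.

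**The path to 24.** Level 1 has 0 DLTs in 3. Level 2 is exceeded with 6. Level 1 is filled to 6 under 16.224 and now shows 2 or more DLTs. If that counts as meeting the boundary, levels -1 and -2 can each take 6: 6 + 6 + 6 + 6 = 24. Section 16.21 (2 of at most 6), 16.225 (more than 1 of 6) and 16.452 (2 or more at any level) support testing it. Section 16.224 can also be read as filling an MTD already declared, which leaves 18.

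**Accrual.** N + 45 + 6 − k, where N is phase I size and k = 0 to 6 is the number of MTD patients with DLBCL who count in the 45. Phase I admits all B-cell lymphomas (3.12), so k is not assured.

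**Duration.** On the plan's figures: 2N/3 + 15 months. By accrual rate r = 4 to 5 per month: 2N/3 + (45 − k)/r + 3. The 3 months for evaluation and data entry is an assumption, taken as 15 − 12 from 16.13. For N = 18 the extremes are 12 + 39/5 + 3 = 22.8 and 12 + 45/4 + 3 = 26.25.

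| N | Accrual (k = 6 to 0) | Months, plan's figures | Months, by rate |
|---|---|---|---|
| 12 | 57 to 63 | 23 | 18.8 to 22.25 |
| 15 | 60 to 66 | 25 | 20.8 to 24.25 |
| 18 | 63 to 69 | 27 | 22.8 to 26.25 |
| 24 | 69 to 75 | 31 | 26.8 to 30.25 |

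**Likelihood.** The documents give no expected DLT rate. Assumption: the rates p in the 16.227 table, equal at all levels, with full expansions of 3. For one level:

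- exceeded with 3 patients: a = 3p²(1−p) + p³
- exceeded with 6 patients: b = 3p(1−p)²[1 − (1−p)³]
- escalate: 1 − a − b, which gives 0.906, 0.709, 0.494, 0.309 and 0.172 and agrees with 16.227.

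Suppose no 0-of-3 level filled to 6 after a higher level was exceeded is tested. Then more than 12 patients requires levels 1 and -1 both to fail, and P(>12) = b² + 2ab(1−a). At p = 0.30, a = 0.216 and b = 0.441 × 0.657 = 0.2897, so P(>12) = 0.0839 + 0.0981 = 18.2%. If all such levels are tested, the paths were enumerated exactly.

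| DLT rate | 10% | 20% | 30% | 40% | 50% |
|---|---|---|---|---|---|
| P(>12), filled levels not tested | 0.8% | 7.0% | 18.2% | 26.9% | 27.2% |
| P(>12), filled levels tested | 1.2% | 10.3% | 25.9% | 37.1% | 36.4% |

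With testing, P(24) stays below 1% at every rate.

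**The case against.** The best defence is that these are projections. Sections 16.12 and 16.13 speak of what is expected and projected, the arithmetic is correct for the case that the authors had in mind, and 16.225 lets the study team re-evaluate the regimen after de-escalation. That makes this an unstated planning condition and keeps it minor. It does not remove the point, because the same sentences use the word maximum, and the discretion in 16.225 comes after the mandatory steps to -1 and -2.

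The likelihood can also be pressed down, and this stands. Levels -1 and -2 give less drug, so equal DLT rates overstate repeated failure. Some paths beyond 12 find no MTD, and phase II as planned would then not open. Section 16.223 allows up to 3 more patients and 16.452 stops accrual to a level at 2 DLTs. If patients enter singly and accrual stops at the second DLT, 18 is still possible, but with probability of at most about 0.2% on the same rates.

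A reader might infer that 63 patients and 2 years fail whenever phase I exceeds 12. The documents do not support that. Overlap can absorb the excess: 15 fits within 63 if at least 3 of the 6 patients at the MTD have DLBCL, and 18 fits if all 6 do. Faster accrual can keep 15, and sometimes 18, within 24 months. Nor is 24 established as the maximum, since it depends on one of two readings of 16.224. Neither 18 nor 24 is an absolute ceiling, because re-escalation is uncounted.

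**Conclusion.** The point holds as a minor error in a stated figure. Twelve is not the phase I maximum under the written rules: 18 is reachable from 16.223 and 16.225 alone, and 24 if levels filled under 16.224 are re-tested. The 63 patients and 2 years are assured as maxima only when phase I uses 12 or fewer. With 18, accrual is up to 6 above the stated 63, and duration is 27 months on the plan's own figures or about 23 to 26 months by accrual rate, the latter resting on the assumed 3 months. Exceeding 12 is unlikely at low DLT rates (about 1% at a 10% rate) and not negligible at 30% or more, on the flat-rate assumption. A reader might fear for the phase II inference. The 20 and 45 patient decision rule, its alpha and its power do not depend on the phase I count and are unaffected.

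**What to change.** - **16.12:** say that 9 to 12 evaluable patients and 63 in total are the expected case and assume that phase I uses no more than 12. Add that the written de-escalation rules can reach 18 (total accrual up to 69), excluding any re-escalation under 16.225.
- **16.13:** put the same condition on 6 to 8 months and 2 years, and say that 18 phase I patients would take about 23 to 27 months.
- **16.224:** reconcile it with 16.21, 16.225 and 16.452 on whether a level filled to 6 is tested again. This review takes no position on which rule is right. If such a level is re-tested, give 24 (accrual up to 75) in place of 18, with about 27 to 31 months in 16.13, so that the plan prints one figure.

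Sections 16.63 and 16.5 need no change, since they already present their figures as expected and estimated. The cost is a few sentences. The expected case and all phase II operating characteristics stay as they are; only the stated maxima become less favourable.
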